#### **Cytology, Histology**

The cytological confirmation of the neoplastic origin of any effusion that appears or worsens during treatment when the measurable tumor has met criteria for response or stable disease (SD) is mandatory to differentiate between response or SD and PD.

### 7.2.4 Response Criteria

#### **Evaluation of Target Lesions**

##### Complete Response

Disappearance of all target lesions, confirmed as permitted by observation on two separate observations conducted not less than 4 weeks apart. Any pathological lymph nodes (whether target or non-target) must have reduction in short axis to <10 mm (the sum may not be "0" if there are target nodes). There can be no appearance of new lesions.

By nature of neoadjuvant study design, responses will be unconfirmed in many patients in this study, as resection will often occur less than 4 weeks after scans.

##### Partial Response

At least a 30% decrease in the sum of the longest diameter (SLD) of target lesions, taking as reference the baseline SLD. There can be no appearance of new lesions.

##### Progressive Disease

At least a 20% increase in the sum of the SLD of target lesions, taking as reference the smallest SLD recorded since the treatment started and minimum 5 mm increase over the nadir, or the appearance of one or more new lesions.

##### Stable Disease

Neither sufficient shrinkage to qualify for PR nor sufficient increase to qualify for PD, taking as reference the smallest SLD since the treatment started.

#### **Evaluation of Non-Target Lesions**

##### Complete Response

Disappearance of all non-target lesions. All lymph nodes must be non-pathological in size (<10 mm short axis).

#### Incomplete Response/Stable Disease

Persistence of one or more non-target lesion(s).

#### Progressive Disease

Appearance of one or more new lesions and/or unequivocal progression of existing non-target lesions.

#### Evaluation of Best Overall Response

The best overall response is the best response recorded from the start of the treatment until PD/recurrence (taking as reference for PD the smallest measurements recorded since the treatment started) or surgical resection. The patient's best response assignment will depend on the achievement of both measurement and confirmation criteria.

**Table 7.1 Response Criteria**

Target Lesions	Non-Target Lesions	New Lesions	Overall Response	Best Response for this Category Also Requires
CR	CR	No	CR	>4 weeks confirmation**
CR	Non-CR/ Non-PD	No	PR	>4 weeks confirmation**
PR	Non-PD	No	PR	
SD	Non-PD	No	SD	Documented at least once >4 weeks from baseline
PD	Any	Yes or No	PD	
Any	PD*	Yes or No	PD	No prior SD, PR or CR
Any	Any	Yes	PD	

\*In exceptional circumstances, unequivocal progression in non-target lesions may be accepted as PD

\*\*Due to neoadjuvant nature of this study, radiographic responses will often be unconfirmed due to surgical resection prior to repeat scans

#### Disease-Free Survival

DFS is defined as the duration of time from surgical resection to time of disease recurrence.

### 7.2 Evaluation of Safety

Analyses will be performed for all patients having received at least one dose of study drug. The study will use the CTCAE v4.03 for reporting of non-hematologic AEs and modified criteria for hematologic AEs.

### 7.3 Definitions of Adverse Events

#### 7.3.1 Adverse Event

An AE (also known as an adverse experience) is defined as any untoward medical occurrence associated with the use of a drug in humans, whether or not considered drug related. More specifically, an AE (can be any unfavorable and unintended sign (e.g., an abnormal laboratory

finding), symptom, or disease temporally associated with the use of a drug, without any judgment about causality. An AE can arise from any use of the drug (e.g., off-label use, use in combination with another drug) and from any route of administration, formulation, or dose, including an overdose.

### **AEs based on signs and symptoms**

All AEs spontaneously reported by the participant or revealed by observation will be collected and recorded in the CRF. When collecting AEs, the recording of diagnoses is preferred (when possible) to the recording list of signs and symptoms. However, if a diagnosis is known and there are other signs or symptoms that are not generally part of the diagnosis, the diagnosis and each sign or symptom will be recorded separately.

### **AEs based on examinations and tests**

Deterioration as compared to baseline in protocol-mandated laboratory values, vital signs, QTc, LVEF, and DLCO should only be reported as AEs if they fulfill any of the SAE criteria or are the reason for discontinuation of treatment with the IP.

If deterioration in a laboratory value/vital sign is associated with clinical signs and symptoms, the sign or symptom will be reported as an AE and the associated laboratory result/vital sign will be considered as additional information. Wherever possible, the reporting Investigator uses the clinical rather than the laboratory term (e.g., anemia versus low Hgb value). In the absence of clinical signs or symptoms, clinically relevant deteriorations in non-mandated parameters should be reported as AE(s).

Deterioration of a laboratory value, which is unequivocally due to PD, should not be reported as an AE/SAE.

Any new or aggravated clinically relevant abnormal medical finding at a physical examination as compared with the baseline assessment will be reported as an AE.

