### 3.4 Duration of Therapy

Patients may receive up to 2 cycles of therapy prior to surgery. Surgery must occur within 14 days of final scans. Patients will continue the study drug following final scans and then discontinue the study drug between 3 and 7 days prior to surgery, and thus may ultimately receive up to two weeks additional therapy with study drug beyond end of cycle 1 (or cycle 2) while awaiting surgery. No treatment with the study drug will be given after surgery.

Criteria for treatment with Cycle #2:

- No Grade 3 or higher AEs with Cycle #1
- No evidence of PD by RECIST 1.1 criteria at end of Cycle #1 scan.
- Additional reduction in tumor size deemed to be potentially beneficial by thoracic surgeon planning to perform resection.

Treatment may be stopped for any of the following reasons:

- The patient or legally authorized representative withdraws consent.
- Any AE that in the opinion of the investigator would pose an unacceptable safety risk to the patient.
- Closure of the study.

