### 8.3.3 Secondary Analysis (or Analysis of Secondary Endpoints)

**5-Year DFS:** DFS will be calculated as 1+ the number of days from date of surgical resection to documented radiographic relapse/progression or death due to any cause over a period of 60 months. The Kaplan-Meier analysis will be used to calculate the median DFS with 95% confidence interval. 5-year DFS rate will be calculated as the percentage of patients who are disease free at 5 years. This will be calculated using the Kaplan-Meier method.

Assuming alpha of 0.05 and a set sample size of 27, as well as a null hypothesis of 50% 5-year DFS [53], we will have a power of 80% to detect a 25% increase in 5-year DFS.

**Objective Response Rate:** The objective response rate is defined as the best overall response recorded from the start of the treatment until time of surgery. The frequency and percentages of patients with a best ORR of CR, PR, SD, or PD will be determined. The objective response rate will be reported with 95% confidence intervals.

**Pathologic Complete Response Rate (pCR):** The pCR is defined as absence of (0%) viable tumor present histologically in the resected tumor specimen. Scoring for pathologic response is described above.

**5-Year Overall survival (OS) rate:** 5-year OS rate will be calculated using the Kaplan-Meier method. OS will be defined as the 1+ the number of days from surgical resection to death due to any cause over a period of 60 months. The Kaplan-Meier analysis will be used to calculate the median OS with 95% confidence interval.

**Depth of Response (DpR):** DpR will be defined as the percentage change in tumor burden by RECIST criteria at best response versus baseline imaging. DpR will be summarized using descriptive statistics and correlated with patient outcomes using hazard ratios via the Cox proportional hazards model.

**Safety and Tolerability:** AE terms recorded on the CRFs will be mapped to preferred terms using the MedDRA. Seriousness, severity grade and relationship to study treatment will be assessed by the investigator. Severity grade will be defined by the NCI CTCAE v4.03. Listings of AEs will be provided. Rate of conversion from operable to non-operative will be recorded as rate of patients initially assessed as surgically resectable, who are subsequently unable to undergo surgical resection due to either treatment-related AEs or PD. Rate of surgical complications occurring prior to the end of treatment visit will be recorded.

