## **Review and Oversight Requirements**

### **Adverse Event Monitoring**

All Grade 3-5 adverse events (AEs), regardless of being unexpected or considered to be associated with the use of the study drug will be entered into OnCore®, UCSF's Clinical Trial Management System.

Adverse events are graded according to the Common Terminology Criteria for Adverse Events (CTCAE) as developed and revised by the Common Therapy Evaluation Program (CTEP) of the National Cancer Institute. Adverse events are further given an assignment of attribution or relationship to the investigational agent(s) or study procedure. Attribution categories are:

- **Definite** – The adverse event is clearly related to the investigational agent(s) or study procedure.
- **Probable** – The adverse event is likely related to the investigational agent(s) or study procedure.
- **Possible** – The adverse event may be related to the investigational agent(s) or study procedure.
- **Unrelated** – the adverse event is clearly not related to the investigational agent(s) or study procedure.

All Grade 3-5 adverse events entered into OnCore® will be reviewed on a monthly basis at the UCSF Site Committee meetings. All adverse events entered into OnCore® will be reviewed on a monthly basis at the UCSF Coordinating Center Site Committee meetings. All grade 3-5 adverse events must be reported to the UCSF Coordinating Center by the participating sites within 10 business days of becoming aware of the event

or during the next scheduled monthly conference call, whichever is sooner. The UCSF Site Committee will review and discuss the selected toxicity, the toxicity grade, and attribution assignment from the UCSF Coordinating Center and the participating sites.

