**Review of Adverse Event Rates**

If an increase in the frequency of Grade 3 or 4 adverse events (above the rate reported in the Investigator Brochure or package insert) is noted in the study, the Study Chair at the UCSF Coordinating Center is responsible for notifying the DSMC Chair (or Vice Chair) and the DSMC Director at the time the increased rate is identified via a report. The report will indicate if the incidence of adverse events observed in the study is above the range stated in the Investigator Brochure or package insert.

If at any time the Study Chair stops enrollment or stops the study due to safety issues, the DSMC Chair (or Vice Chair) and the DSMC Director must be notified within one business day and the IRB must be notified within their reporting guidelines.

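### Non-serious grade 3 laboratory and QTc abnormalities that do not end treatment are not reported as AEs, so the comparison with brochure grade 3-4 rates is biased low for those items and for the overall rate

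*Combined protocol and SAP*

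**What the plan says.** **Reporting.** Section 7.3.1 defines an AE broadly: it "can be any unfavorable and unintended sign (e.g., an abnormal laboratory" finding. Its subsection on examinations and tests then narrows this. The narrowing covers measurements that the protocol itself mandates (laboratory tests, vital signs, QTc, LVEF and DLCO). When these deteriorate from baseline, the rule is that they "should only be reported as AEs if they fulfill any of the SAE criteria or are the reason for discontinuation of treatment". Where symptoms accompany the change, "the sign or symptom will be reported as an AE and the associated laboratory result/vital sign will be considered as additional information". For parameters that the protocol does not mandate, clinically relevant deteriorations without symptoms are reportable.

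**Provisions that use AEs.**
- Appendix 3, Review of Adverse Event Rates, obliges the Study Chair to notify the DSMC: "If an increase in the frequency of Grade 3 or 4 adverse events (above the rate reported in the Investigator Brochure or package insert").
- Appendix 3, Adverse Event Monitoring, has these entered and reviewed monthly: "All Grade 3-5 adverse events (AEs), regardless of being unexpected". Section 7.4 has the same entry rule for grade 3 and above.
- Section 3.4 makes this a condition for the second cycle: "No Grade 3 or higher AEs with Cycle #1".

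**Analysis.** Section 2.4.2 and Table 8.1 make CTC-graded laboratory and ECG abnormalities a secondary endpoint beside AEs. The safety paragraph of 8.3.3 maps AE terms to MedDRA and says "Listings of AEs will be provided". Section 8.4 adds only the population and CTCAE v4.03. The Abstract and Section 7.2 instead refer to "modified criteria for hematologic AEs", which are defined nowhere.

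**The concern.** A comparison with an external rate needs both sides to count the same events. Table 4.4, the protocol's brochure-based list of adverse reactions, includes platelet, leucocyte and neutrophil decreases and QTc prolongation, with grade 3+ rates. The trial would report such events as AEs only when they are serious or end treatment. A true excess in these items could then go unflagged.

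There are two further consequences. It is unclear whether a grade 3 laboratory or QTc value that was not reported as an AE counts against the Cycle 2 condition in 3.4. And a named secondary endpoint has no analysis that would produce it.

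**Working it through.** The plan states no figure on this point, so there is nothing to reproduce. The check is a trace through the text, then a sizing from Table 4.4.

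**1. Trace of one event.** Take a QTc of 501 ms or more, grade 3 in Table 5.5, that is held, recovers and is resumed, with no SAE criterion met.
- AE definition (7.3.1): an abnormal finding can be an AE.
- Examinations-and-tests rule (7.3.1): not reported, because it is neither serious nor the reason for discontinuation.
- Table 5.5: dosing is still interrupted, because that rule acts on the measured QTc.
- Appendix 3 rate comparison and monthly review: not counted, because both use AEs.
- Section 3.4: undetermined, because it refers to AEs without saying which of the two 7.3.1 rules applies.

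An asymptomatic, non-serious grade 3 neutrophil decrease that is held and resumed follows the same path.

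**2. Size at the reference rates.** Inputs: grade 3+ rates from Table 4.4; n = 27 from Section 3.2. Expected count = 27 × p; chance of at least one = 1 − (1 − p)^27.

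| Item | p | Expected | At least one |
|---|---|---|---|
| Neutrophils decreased | 4.3% | 1.16 | 69% |
| Leucocytes decreased | 2.4% | 0.65 | 48% |
| Platelets decreased | 2.1% | 0.57 | 44% |
| QTc prolongation | 0.7% | 0.19 | 17% |

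For neutrophils: 1 − 0.957^27 = 0.69. The rows may overlap within a patient. The chance of at least one patient with any of the four lies between 69% (full overlap) and 1 − (1 − 0.095)^27 = 93% (no overlap; 4.3 + 2.4 + 2.1 + 0.7 = 9.5%).

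These rates come from the AURA studies, and exposure here is at most 70 days (Abstract). If the neutrophil rate over that exposure were half or a quarter of the reference, the chance of at least one event would be 1 − 0.9785^27 = 44% or 1 − 0.98925^27 = 25%. Those two fractions are assumptions.

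**3. Effect on the comparison.** Appendix 3 gives no threshold or test, so I take an excess to mean an observed proportion above the reference. For neutrophils, 1/27 = 3.7% is below 4.3% and 2/27 = 7.4% is above it, so two recorded cases are needed. Suppose the true rate is double the reference (8.6%) and a share f of events is still reportable under 7.3.1. The chance of two or more recorded cases, with rate 0.086 × f and n = 27, is:

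| f | 1 | 0.5 | 0.25 | 0.1 | 0 |
|---|---|---|---|---|---|
| Chance | 69% | 32% | 11% | 2% | 0% |

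The documents do not give f, so this is a range, not an estimate.

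**4. Does the reference count such events?** The documents do not say how the brochure rates were recorded. Table 4.4 gives leucocytes decreased at any grade in 66%, while Section 1.2.1 gives SAEs of all kinds in 26.0% of patients. The sources differ (phase II and III against phase II), and no discontinuation rate is given. Still, 66% is hard to obtain under a rule of serious or treatment-ending only. This bears on the recording convention; it does not directly establish how the grade 3+ events were handled.

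**5. Endpoint against analysis.** Section 2.4.2 and Table 8.1 name graded laboratory and ECG abnormalities. Sections 8.3.3 and 8.4 describe AE terms, AE listings, conversion to inoperable status and surgical complications. No step grades or tabulates laboratory or ECG values.

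**The case against.** The strongest reply is that most of the protection lies outside AE reporting, and much of it does.

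- Section 5.2 interrupts dosing on CTCAE grade or toxicity, and Tables 5.5 and 5.7 act on measured QTc and glucose or on clinical findings. A reader might infer that these abnormalities drop out of dose management. They do not.
- Section 5.3 lists prolonged QTc, ejection-fraction changes, liver chemistry elevations and hyperglycemia as AEs of special interest, and asks that management of grade 3 or higher toxicity be discussed with the PI. Under Appendix 3 the PI at the coordinating center is the Study Chair, who issues the notification and so should usually know of such events. That stands, but it does not put them into the rate being compared.
- Some severe events remain reportable because they end treatment: grade 4 events and delays over two weeks under Table 5.3, recurrent grade 3 or any grade 4 QTc prolongation under Table 5.5. The loss is therefore partial and of unknown size.
- Symptom-based events are collected in full, so ILD, diarrhea and rash rates remain comparable. A reader might infer that no AE rate can be compared; the text does not support that. For LVEF, Table 4.4 gives no rate to compare with.
- A reader might also infer that most grade 3+ events would be lost, because laboratory and QTc rows make up 9.5 of 12.5 summed percentage points (76%) in Table 4.4. That sum adds possibly overlapping rows from a selected list. Section 1.2.1 reports 36.3% of patients with a grade 3+ AE, against which 9.5 points is about 26%, from a different source. Neither figure measures the loss.
- The graded laboratory and ECG endpoint exists, and 8.3.1 says in general terms that categorical measurements are summarized by frequency and percentage. But nothing says that a worst-grade table will be made, or that Appendix 3 or 3.4 draws on one.

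**Conclusion.** The concern holds within limits. The examinations-and-tests rule conflicts with the AE definition in 7.3.1. Followed as written, it biases the trial's grade 3-4 AE frequency low against the brochure for laboratory and QTc items and for the overall grade 3+ rate. The missing events are not remote: about a 69% chance of at least one grade 3+ neutrophil event in 27 patients, if the Table 4.4 rate applies to this population and short exposure. How many would still be reported is not given. The direction of bias also assumes that the brochure rates include non-serious events that did not end treatment, which Table 4.4 suggests but does not state.

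Separately, the laboratory and ECG part of the secondary safety endpoint has no specific analysis, and the hematologic grading standard differs between the Abstract and 7.2 on one side and 8.3.3 and 8.4 on the other. The primary endpoint is unaffected. The appendix provision is a notification duty, not a formal test, and continuous review by the PI and DSMC goes on regardless. The change should be made, but it does not put the trial's main conclusion at risk.

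**What to change.** - **Sections 8.3.3 and 8.4:** derive CTCAE v4.03 grades from the laboratory and QTc values already collected under Appendix 1, and tabulate the worst grade per patient among all treated patients.
- **Appendix 3, Review of Adverse Event Rates:** state that the comparison uses these derived grades together with reported AE terms.
- **Abstract and Section 7.2:** replace the undefined modified hematologic criteria with the CTCAE v4.03 grading used in 8.3.3 and 8.4.
- **Sections 7.3.1 and 3.4:** reconcile the examinations-and-tests rule with the AE definition and with the Cycle 2 condition, so that it is clear whether a grade 3 laboratory or QTc value counts for that condition. Which rule applies is a clinical decision for the sponsor; none is proposed here.

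The cost is one derived table and some wording, with no new assessments. The reported grade 3-4 rate may look less favourable than it would under the present rule.

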#### **7.3.2 Adverse reaction**

An adverse reaction is defined as any AE caused by the use of a drug. Adverse reactions are a subset of all suspected adverse reactions for which there is reason to conclude that the drug caused the event.

##### **7.3.2.1 Suspected**

A suspected adverse reaction is defined as any AE for which there is a reasonable possibility that the drug caused the AE. For the purposes of IND safety reporting, "reasonable possibility" indicates that there is evidence to suggest a causal relationship between the drug and the AE. A suspected adverse reaction implies a lesser degree of certainty about causality than an adverse reaction.

##### **7.3.2.2 Unexpected**

An AE or suspected adverse reaction is considered *unexpected* if it is not listed in the investigator brochure or package insert(s), or is not listed at the specificity or severity that has been observed, or, if an investigator brochure is not required or available, is not consistent with the risk information described in the general investigational plan or elsewhere in the current application.

"Unexpected," as used in this definition, also refers to AEs or suspected adverse reactions that are mentioned in the investigator brochure as occurring with a class of drugs or as anticipated

from the pharmacological properties of the drug, but are not specifically mentioned as occurring with the particular drug under investigation.

AEs that would be anticipated to occur as part of the disease process are considered *unexpected* for the purposes of reporting because they would not be listed in the investigator brochure. For example, a certain number of non-acute deaths in a cancer trial would be anticipated as an outcome of the underlying disease, but such deaths would generally not be listed as a suspected adverse reaction in the investigator brochure.

Some AEs are listed in the Investigator Brochure as occurring with the same class of drugs, or as anticipated from the pharmacological properties of the drug, even though they have not been observed with the drug under investigation. Such events would be considered *unexpected* until they have been observed with the drug under investigation. For example, although angioedema is anticipated to occur in some patients exposed to drugs in the ACE inhibitor class and angioedema would be described in the investigator brochure as a class effect, the first case of angioedema observed with the drug under investigation should be considered *unexpected* for reporting purposes.

